11.2.3 Expectedness

Adverse events can be 'Expected' or 'Unexpected.'

11.2.3.1 Expected adverse event

Expected adverse events are those that have been previously identified as resulting from administration of adjuvant radiation treatment. For the purposes of this study, an adverse event is considered expected when it is included in the informed consent document as a potential risk.

Refer to Section 6.1 (Anticipated Toxicities) for a listing of expected adverse events associated with the study treatment.

11.2.3.2 Unexpected adverse event

For the purposes of this study, an adverse event is considered unexpected when it varies in nature, intensity or frequency from information provided in the informed consent document or when it is not included in the informed consent documentation as a potential risk.

11.2.4 Attribution

Attribution is the relationship between an adverse event or serious adverse event and the study treatment. Attribution will be assigned as follows:

- Definite – The AE is clearly related to the study treatment.
- Probable – The AE is likely related to the study treatment.
- Possible – The AE may be related to the study treatment.
- Unlikely - The AE is doubtfully related to the study treatment.
- Unrelated - The AE is clearly NOT related to the study treatment.

11.3 Recording Adverse Events

CONFIDENTIAL

This document is confidential. Do not disclose or use except as authorized.

Adverse event information will be obtained at each contact with the participant. All adverse events will be recorded on the appropriate study-specific case report forms (CRFs).

11.4 Reporting Adverse Events

Each adverse event will be assessed to determine if it meets the criteria for serious adverse event. If a serious adverse event occurs, expedited reporting will follow local policies, and federal guidelines and regulations as appropriate.

It is the responsibility of the participating investigator to notify the Principal Investigator (or Protocol Chair), IRB, and others of all serious adverse events as required in the protocol.

The Principal Investigator (or Protocol Chair) will provide information with respect to adverse events and safe use of the study treatment (e.g., safety reports, Action Letters) to all participating investigators as soon as the information becomes available.

11.4.1 Serious Adverse Event Reporting Requirements

All events meeting the criteria for Serious Adverse Event (see Section 11.2.2) that occur after the initial dose of study treatment, during treatment, or within 30 days of the last dose of treatment must be reported as serious adverse events.

The participating investigator must report each serious adverse event, regardless attribution, to the Principal Investigator (or Protocol Chair) within 24 hours of learning of the occurrence. In the event that the participating investigator does not become aware of the serious adverse event immediately (e.g., participant sought treatment elsewhere), the participating investigator is to report the event within 24 hours after learning of it and document the time of his or her first awareness of the adverse event. Report serious adverse events by telephone and facsimile to:

[name] [contact] [contact]

Within the following 24-48 hours, the participating investigator must provide follow-up information on the serious adverse event. Follow-up information should describe whether the event has resolved or continues, if and how the event was treated, and whether the participant will continue or discontinue study participation.

11.4.2 Non-Serious Adverse Event Reporting Requirements

Non-serious adverse events will be reported to the Principal Investigator (or Protocol Chair) on the toxicity Case Report Forms.

CONFIDENTIAL

This document is confidential. Do not disclose or use except as authorized.

11.5 Institutional Review Board (IRB) Notification by Investigator

The participating investigator will report all adverse events and serious adverse events to the Principal Investigator (or Protocol Chair) and to the IRB according to the local IRB's policies and procedures in reporting adverse events.

11.6 Hospital Risk Management Notification by Investigator

The participating investigator will report to the Principal Investigator (or Protocol Chair) and to local Risk Management any subject safety reports or sentinel events that require reporting according to institutional policy.

12. DATA AND SAFETY MONITORING

12.1 Data Reporting

12.1.1 Method

The ODQ will collect, manage, and monitor data for this study.

12.1.2 Data Submission

The schedule for completion and submission of case report forms (paper or electronic) to the ODQ is as follows:

Form	Submission Timeline
Eligibility Checklist	Complete prior to registration with ODQ
On Study Form	Within 14 days of registration
Baseline Assessment Form	Within 14 days of registration
Treatment Form	Within 10 days of the last day of the treatment
Toxicity Form	Weekly during treatment; within 14 days of protocol defined follow-up visit
Lab Form	With Baseline assessment form and weekly during treatment
Adverse Event Report Form	Immediately upon detection of adverse event

CONFIDENTIAL

This document is confidential. Do not disclose or use except as authorized.

	during treatment. Within 14 days of adverse event detected during surveillance follow-up.
Off Treatment/Off Study Form	Within 14 days of being taken off study for any reason
Follow up/Survival Form	Within 14 days of the protocol defined follow up visit date or call

12.2 Safety Meetings

The DF/HCC Data and Safety Monitoring Committee (DSMC) will review and monitor toxicity and accrual data from this trial. The committee is composed of clinical specialists with experience in oncology and who have no direct relationship with the study. Information that raises any questions about participant safety will be addressed with the Principal Investigator and study team.

The DSMC will meet as needed to review toxicity and accrual data. Information to be provided to the committee may include: up-to-date participant accrual;; all grade 2 or higher unexpected adverse events that have been reported; summary of all deaths occurring within 30 days for Phase I or II protocols; for gene transfer protocols, summary of all deaths while being treated and during active follow-up; any response information; audit results, and a summary provided by the study team. Other information (e.g. scans, laboratory values) will be provided upon request.

12.3 Monitoring

Involvement in this study as a participating investigator implies acceptance of potential audits or inspections, including source data verification, by representatives designated by the Principal Investigator (or Protocol Chair) or DF/HCC. The purpose of these audits or inspections is to examine study-related activities and documents to determine whether these activities were conducted and data were recorded, analyzed, and accurately reported in accordance with the protocol, institutional policy, Good Clinical Practice (GCP), and any applicable regulatory requirements.

All data will be monitored for timeliness of submission, completeness, and adherence to protocol requirements. Monitoring will begin at the time of participant registration and will continue during protocol performance and completion.

13. REGULATORY CONSIDERATIONS

13.1 Protocol Review and Amendments

CONFIDENTIAL

This document is confidential. Do not disclose or use except as authorized.

This protocol, the proposed informed consent and all forms of participant information related to the study (e.g., advertisements used to recruit participants) and any other necessary documents must be submitted, reviewed and approved by a properly constituted IRB governing each study location.

Any changes made to the protocol must be submitted as amendments and must be approved by the IRB prior to implementation. Any changes in study conduct must be reported to the IRB. The Principal Investigator (or Protocol Chair) will disseminate protocol amendment information to all participating investigators.

All decisions of the IRB concerning the conduct of the study must be made in writing.

13.2 Informed Consent

All participants must be provided a consent form describing this study and providing sufficient information for participants to make an informed decision about their participation in this study. The formal consent of a participant, using the IRB approved consent form, must be obtained before the participant is involved in any study-related procedure. The consent form must be signed and dated by the participant or the participant's legally authorized representative, and by the person obtaining the consent. The participant must be given a copy of the signed and dated consent document. The original signed copy of the consent document must be retained in the medical record or research file.

13.3 Ethics and Good Clinical Practice (GCP)

This study is to be conducted according to the following considerations, which represent good and sound research practice:

- ICH Consolidated Good Clinical Practice: Guidelines (E6)
www.fda.gov/cder/guidance/iche6.htm
- US Code of Federal Regulations (CFR) governing clinical study conduct and ethical principles that have their origin in the Declaration of Helsinki
- Title 21 Part 11 – Electronic Records; Electronic Signatures
www.access.gpo.gov/nara/cfr/waisidx_02/21cfr11_02.html
- Title 21 Part 50 – Protection of Human Subjects
www.access.gpo.gov/nara/cfr/waisidx_02/21cfr50_02.html

CONFIDENTIAL

This document is confidential. Do not disclose or use except as authorized.

- Title 21 Part 54 – Financial Disclosure by Clinical Investigators
www.access.gpo.gov/nara/cfr/waisidx_02/21cfr54_02.html
- Title 21 Part 56 – Institutional Review Boards
www.access.gpo.gov/nara/cfr/waisidx_02/21cfr56_02.html
- Title 21 Part 312 – Investigational New Drug Application
www.access.gpo.gov/nara/cfr/waisidx_02/21cfr312_02.html
- State laws
- Institutional research policies and procedures www.dfhcc.harvard.edu/clinical-research-support/clinical-research-operations-cro/policies-and-procedures

It is understood that deviations from the protocol should be avoided, except when necessary to eliminate an immediate hazard to a research participant. In such case, the deviation must be reported to the IRB according to the local reporting policy.

13.4 Study Documentation

The investigator must prepare and maintain adequate and accurate case histories designed to record all observations and other data pertinent to the study for each research participant. This information enables the study to be fully documented and the study data to be subsequently verified.

Original source documents supporting entries in the case report forms include but are not limited to hospital records, clinical charts, laboratory and pharmacy records, recorded data from automated instruments, microfiches, photographic negatives, microfilm or magnetic media, and/or x-rays.

13.5 Records Retention

All study-related documents must be retained for the maximum period required by applicable federal regulations and guidelines or institutional policies.

13.6 Multi-center Guidelines: N/A

14. STATISTICAL CONSIDERATIONS

CONFIDENTIAL

This document is confidential. Do not disclose or use except as authorized.

The primary objective of this protocol is to determine whether the substitution of scanning pencil beam proton teletherapy for conventional photon teletherapy will administer less radiation dose to the normal tissues of organs at risk compared to conventional techniques (IMRT or 3-D conformal teletherapy). Additional endpoints are to determine whether scanning pencil beam proton teletherapy is associated with cancer control rates within the irradiated volumes comparable to those reported in existing literature and to determine the rates of acute radiation side effects and delayed radiation complications.

14.1 Study Design/Endpoints:

The primary endpoint is the comparison of dose volume histograms (DVH) from proton teletherapy and conventional photon teletherapy. Structure sets contoured for proton beam treatment will be used to plan alternative IMRT and 3DCRT plans by the same medical physics team and attending physician, and DVH will be generated for each plan. It is hypothesized that the area under the DVH curve will be at least 25% smaller in the bowel, in favor of the proton plan, for virtually all patients. With a sample size of 22 patients, we will have 91% power to accept that the proton plan is superior for 95% of patients if at least 20 of them have a proton plan with an area under the DVH curve at least 25% smaller in the bowel. The decision rule is associated with type 1 error of 15% if only 80% of patients truly have a superior proton plan for the bowel. This magnitude of radiation dose difference is expected to be clinically significant with respect to acute GI side effects, thus GI toxicities will be a major focus of the data analysis to explore the correlation between DVH and radiation effects.

14.2 Sample Size/Accrual Rate:

As of October 2016, 9 node positive uterine cancer patients and 5 node positive cervical cancer patients have been enrolled and treated with proton beam teletherapy. We project another 8 patients will be enrolled and treated by the end of 2018 for a total accrual of 22 patients. Based on the tumor distribution to date, we expect the final accrual will consist of approximately 14 uterine cancer patients and 8 cervical cancer patients. Patients who do not start protocol treatment will be replaced.

All patients will be followed for a minimum of 60 months following completion of protocol therapy.

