Using data from the same treatment planning CT scans used to plan proton therapy, conventional photon plans will be generated using three dimensional conformal radiation therapy (3DCRT) and intensity modulated radiation therapy (IMRT) for comparison purposes to quantitate the extent of normal tissue sparing through the use of dose volume histograms.

Monitoring during and after such treatment will be essentially equivalent to standard clinical practice at MGH with the exception that the schedule of post-treatment assessments will more tightly conform to the study calendar.

Assuming successful accrual and treatment of sufficient numbers of patients, a retrospective outcomes study will compare cancer control within the irradiated volume, acute side effects of teletherapy, and delayed complications of radiation treatment to a historical control population treated with photon teletherapy at MGH.

CONFIDENTIAL

This document is confidential. Do not disclose or use except as authorized.

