1.2 Primary Objective

1.2.1 In a population of women with cancers of the cervix or endometrium with pathologically proven spread to regional lymph nodes, to quantitate the magnitude of the normal tissue radiation dose reductions achieved by comparison of dose volume histograms achieved by scanning proton beam teletherapy with dose volume histograms of treatment plans for the same patients using 3-dimensional conformal radiation therapy (3DCRT) and intensity modulated radiation therapy (IMRT).

1.2.2 To prospectively assess acute radiation side effects and delayed complications in proton treated patients and to compare toxicity outcomes (acute side effects and delayed complications) with patients historically treated with photon teletherapy using institutional historical controls (retrospective outcomes comparison study).

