5.2 Agent Administration

CONFIDENTIAL

This document is confidential. Do not disclose or use except as authorized.

5.2.1 Proton beam therapy will be planned based on patient supine CT simulation with custom immobilization per standard practice in the Department of Radiation Oncology, Massachusetts General Hospital.

5.2.2 Full contours will be obtained for all abdominal organs at risk including: stomach, duodenum, bowel (small bowel will be contoured separately if patient requires boost with teletherapy), rectum, liver, kidneys, spinal cord, thoraco-lumbar spine T12-L5, pelvic bone girdle, and proximal femurs from the femoral heads to below the lesser trochanters.

5.2.3 Comparative treatments plans for IMRT and 3DCRT will be generated for each participant from the same CT-simulation data set for comparison purposes and for actual treatment of participants in the event of the proton beam being unavailable for any reason longer than 2 working days.

5.2.4 Standard immobilization-stabilization procedures and treatment verification procedures will be employed as customarily performed for patients at the FHBPTC.

5.2.5 For participants undergoing proton beam therapy to the pelvis, the superior extent of the target volume will be at the interspace of the fifth lumbar vertebra and the first sacral segment (L5-S1).

5.2.6 For participants undergoing proton beam therapy to an extended volume (pelvic and para-aortic nodal basins) the superior border will be at the interspace of the twelfth thoracic and the first lumbar vertebrae (T12-L1).

5.2.7 For participants treated for cervical cancer the inferior extent of the target volume will encompass the proximal 2 cm of the vagina.

5.2.8 For participants treated for uterine cancer, the inferior extent of the target volume will encompass the full extent of the vagina from the apex to the introitus defined as the external urethral meatus.

5.2.9 All proton beam teletherapy treatments will be administered at a daily dose of 1.8 Gy (RBE). The RBE for proton radiation is set at 1.1. The dose unit Gy (RBE) is defined as the proton dose in Gy x RBE 1.1.

5.2.10 All proton beam teletherapy treatments will be administered no more than 5 treatment days per week.

5.2.11 Total absorbed teletherapy dose will be 45 Gy (RBE) in 25 daily fractions of 1.8 Gy (RBE) over 6 weeks for all participants except as noted in 5.2.12.

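### Section 14.1 presents 95% as the conclusion of a 20-of-22 rule that controls error only at 80%, does not name the photon reference for the 25% criterion, and plans no estimate of the magnitude that objective 1.2.1 asks for

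*Combined protocol and SAP*

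**What the plan says.** The primary endpoint in section 14.1 is a comparison of dose volume histograms (DVH). "It is hypothesized that the area under the DVH curve will be at least 25% smaller in the bowel", in favour of protons, for nearly every patient. The decision rule follows: with 22 patients, "we will have 91% power to accept that the proton plan is superior for 95% of patients if at least 20 of them" meet that criterion. The next sentence gives the error rate: "type 1 error of 15% if only 80% of patients truly have a superior proton plan for the bowel".

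On the comparator, section 14.1 says "Structure sets contoured for proton beam treatment will be used to plan alternative IMRT and 3DCRT plans", and section 5.2.3 says "Comparative treatments plans for IMRT and 3DCRT will be generated for each participant from the same CT-simulation data set". So every patient has two photon plans. The opening paragraph of section 14 describes the comparison as "compared to conventional techniques (IMRT or 3-D conformal teletherapy"), whereas objective 1.2.1 names 3DCRT and IMRT together.

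On what is to be learned, objective 1.2.1 is "to quantitate the magnitude of the normal tissue radiation dose reductions achieved", and section 1.1 says that the photon plans serve "to quantitate the extent of normal tissue sparing through the use of dose volume histograms". Section 14 restates the primary objective as a question of whether protons give less dose to organs at risk. Section 14.4 covers only quality of life, progression-free survival and patterns of recurrence. Section 15.1.2 promises a publication comparing the three sets of DVHs but names no summary statistic or interval.

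**The concern.** Three things in the primary analysis do not fit together.

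- **Conclusion.** Read literally, a pass entitles the trial to say that protons are superior for 95% of patients. The rule has no error control at 95%; its only stated error rate is at 80%. The 95% claim is the one conclusion that section 14.1 attaches to a pass, so it is the one most likely to be carried into a report.
- **Comparator.** The organ, metric, threshold and direction of the per-patient event are all fixed. The photon reference is not: it could be IMRT, 3DCRT, either or both. Left open, it could be settled after the DVHs have been seen.
- **Magnitude.** A yes/no count scores a 26% reduction and a 60% reduction the same. It cannot deliver the size of the sparing that objective 1.2.1 and section 1.1 ask for.

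**Working it through.** **Inputs (section 14.1):** n = 22; pass if X ≥ 20; planning alternative 0.95; null value 0.80. X is the number of patients meeting the bowel criterion, taken as binomial.

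**1. Reproduce the plan's figures.** P(X ≥ 20 | p) = 231·p^20·(1−p)^2 + 22·p^21·(1−p) + p^22.

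- At p = 0.95: 0.2070 + 0.3746 + 0.3235 = 0.9052. The plan prints 91%.
- At p = 0.80: 0.1065 + 0.0406 + 0.0074 = 0.1545. The plan prints 15%.

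Both agree. The neighbouring cut-offs do not: 19 or more gives 33.2% error and 97.8% power, and 21 or more gives 4.8% and 69.8%.

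**2. How often the rule passes when the true share is below 95%.**

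| True share | P(pass) |
|---|---|
| 75% | 6.1% |
| 80% | 15.4% |
| 85% | 33.8% |
| 90% | 62.0% |
| 95% | 90.5% |

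**3. What each passing result supports (exact Clopper-Pearson limits).**

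| Result | One-sided lower limit at the rule's 15.4% level | One-sided 95% lower limit | Two-sided 95% CI |
|---|---|---|---|
| 20/22 (90.9%) | 80.0% | 74.1% | 70.8% to 98.9% |
| 21/22 (95.5%) | 85.6% | 80.2% | 77.2% to 99.9% |
| 22/22 (100%) | 91.9% | 87.3% | 84.6% to 100% |

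For 22/22 the limit at the rule's level is 0.1545^(1/22) = 0.919. No row reaches 95%. With every patient a success, a lower limit of 95% needs n ≥ ln(0.1545)/ln(0.95) = 36.4, so 37 patients, at the rule's level. At a one-sided 5% level it needs ln(0.05)/ln(0.95) = 58.4, so 59.

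**4. Why the comparator matters.** The printed error rates hold for whichever single event is defined. Suppose instead that 95% and 80% describe each comparator separately (an assumption; the plan does not say).

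- Both must be beaten, 95% each: the joint share lies between 1 − (0.05 + 0.05) = 90% and 95%, so power lies between 62.0% and 90.5% (63.6% if independent).
- Either suffices, 80% each: the share meeting at least one lies between 80% and 100%, so the pass probability lies between 15.4% and 100% (94.4% if independent).

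**5. Precision of a paired estimate.** The 95% CI half-width for a mean of 22 paired differences is t(0.975, 21)/√22 = 0.443 SD. The documents give no SD. If it were 10 to 20 percentage points (assumed), the half-width would be about 4.4 to 8.9 points.

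**The case against.** The strongest reply is that giving power to accept the design alternative is common shorthand for a single-arm rule. Sample size, cut-off, null, alternative, power and error are all printed and all reproduce, and the 80% value is in the very next sentence. A statistical reader would see what is tested, and section 15.1.2 plans no 95% claim in so many words. All of that is true, and it makes this an error of wording and inference, not of design. It does not rescue the sentence, which still names 95% as what is accepted.

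On the comparator, objective 1.2.1 names both techniques, so a two-comparator reading is available. But section 14 joins them with *or*, and nothing else in the documents resolves the difference.

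On magnitude, the yes/no count does answer the objective as section 14 restates it, at least for bowel. Sections 1.1 and 15.1.2 also show an intention to quantify and compare. What is missing is a named statistic and an interval, so that part is an improvement and not the correction of an error.

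A reader might also infer three stronger things that the documents do not support:

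- That the data can never support more than 80%. This holds for the minimum pass only; 21/22 and 22/22 support more.
- That the whole per-patient event is undefined. Only the photon reference is.
- That the comparator has been, or will be, picked after seeing results. The documents do not say whether any DVHs had been compared.

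**Conclusion.** The point holds in three parts of unequal weight.

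- The conclusion of 95% in section 14.1 is wrong as written. A pass is evidence against a true share of 80% or less at a one-sided 15.4% level. The rule would pass 62% of the time if the true share were 90%.
- The photon reference for the primary event is unspecified, and the choice can change the operating characteristics materially.
- The planned count does not deliver the magnitude in objective 1.2.1. This gap is cheap to fill.

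The binomial figures assume independent patients and a single defined event, and need nothing beyond section 14.1. The comparator ranges and the precision in percentage points rest on the assumptions labelled above. A reader might infer that the sample size or cut-off is miscalculated; it is not, since both printed rates reproduce.

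**What to change.** **1. Correct section 14.1.** Replace the acceptance of 95% with wording such as: *A result of 20 or more out of 22 rejects the hypothesis that 80% or fewer of patients have a bowel DVH area at least 25% smaller with protons than with [named photon comparator] (exact one-sided type I error 15.4%; power 90.5% if the true share is 95%).* Report the observed share with an exact confidence interval. State that the rule works at a one-sided 15.4% level, because a two-sided 95% interval will include 80% at 20/22 and at 21/22.

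**2. Name the comparator event:** IMRT, 3DCRT, or both in the same patient. Section 14.2 puts 9 + 5 = 14 of the 22 patients as already treated by October 2016, and section 5.2.3 requires photon plans for each. So record the date on which the definition is fixed and which DVH comparisons had been seen by then.

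**3. As a cheap improvement,** add the paired per-patient percentage difference in bowel DVH area, as a mean or median with 95% CI, against IMRT and 3DCRT separately. Give the same for the other contoured organs at risk, labelled descriptive.

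The cost is a few sentences, a short analysis of DVHs already planned for every patient, and a less favourable headline claim. Sample size and cut-off are unchanged.
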